#### 7.2.3.1.2 *Serious Adverse events (SAE)*

An SAE is any untoward medical occurrence that at any dose:

- Results in death,
- Is life-threatening,
- Requires inpatient hospitalization or prolongation of existing hospitalization,
- Results in persistent or significant disability/incapacity, or
- Is a congenital anomaly/birth defect.

Important medical events that may not result in death, be life-threatening, or require hospitalization may be considered an SAE when, based upon appropriate medical judgment, they may jeopardize the safety of the subject, and may require medical or surgical intervention to prevent one of the outcomes listed in this definition. Examples of such events are intensive treatment in an emergency room or at home for allergic bronchospasm, blood dyscrasia, or convulsions that do not result in hospitalization.

Note:

The term “life-threatening” refers to an event in which the subject was at risk of death at the time of the event; it does not refer to an event that hypothetically might have caused death if it was more severe.

Inpatient hospitalization is considered to have occurred if the subject has had to stay for a night at the hospital. The criterion for prolongation of hospitalization is also defined as an extra night at the hospital. Hospitalization may not constitute sufficient grounds to be considered as an SAE if it is solely for the purpose of a diagnostic tests (even if related to an AE), elective hospitalization for an intervention that was already planned before subject enrolment in the clinical trial, admission to a day-care facility, social admission (e.g., if the subject has no place to sleep), or administrative admission (e.g., for a yearly examination).

#### 7.2.3.1.3 *Adverse Events of Special Interest (AESIs)*

An AESI is a noteworthy event for the particular study drug that can be appropriate to monitor closely. It could be serious or non-serious and AESIs could include events that might be potential precursors or prodromal symptoms for more serious medical conditions in susceptible individuals.

AEs of special interest for this study are defined as:

1. Typical clinical signs and symptoms consistent with Vitamin D toxicity:
  - polyuria, polydipsia
  - clinically significant mental status changes
2. Out-of-range laboratory result that is identified as clinically significant and related to the study drug
3. Dermatological events such as severe skin irritation as well as severe local and/or generalized pruritus
4. Suspected skin sensitization (contact allergy)
5. Cutaneous AE assessed as related to the study drug and leading to discontinuation of the study drug, including temporary discontinuations

For AESIs, the Investigator is required to complete the Adverse Event Form on the eCRF and follow the AESI reporting procedures in Section [7.2.3.2.3](#) even if the event is considered non-serious according to the usual regulatory criteria.

#### 7.2.3.1.4 *Unexpected adverse drug reaction*

According to ICH E6, an unexpected adverse drug reaction is defined as an adverse reaction, the nature or severity of which is not consistent with the applicable study drug information (e.g., Investigator's Brochure for an unapproved investigational product or the package insert/summary of product characteristics for an approved product).

#### 7.2.3.1.5 *Adverse event reporting period*

The clinical trial period during which AEs must be reported is the period from when the subject signed the Informed Consent Form to the end of the subject's participation.

The Sponsor should be informed if the Investigator becomes aware of any unusual safety information or any safety information that appears to be drug-related involving a subject who has participated in a clinical trial, even after a subject has completed the clinical trial. The Investigator should be diligent in looking for possible latent safety effects that may not appear until a medication has been discontinued.

#### 7.2.3.1.6 *Severity*

Severity is a clinical determination of the intensity of an AE and not of a disease.

The Investigator is to classify the intensity of AEs using the following definitions as a guideline for all AEs occurring during clinical trials conducted or sponsored by GALDERMA. For this classification, the Investigator will take into account the possible range of the intensity of the event and report the grade of intensity which is the most appropriate according to his medical judgment.

Mild	Awareness of signs or symptom, but easily tolerated.
Moderate	Discomfort, enough to cause interference with usual activity
Severe	Incapacitating with inability to work or perform usual activity

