### **1.3 Risk/Benefit assessment**

As mentioned in Section 1 above, calcitriol 3 mcg/g ointment has shown efficacy over vehicle in studies with adult subjects.

The primary objective of this LTS study is to collect long-term (up to 26 weeks) safety data in children 2-16 years and 11 months of age (Version R03). As a secondary objective, calcitriol levels will be assessed at several time points throughout the study duration in a subset of children aged 2 to 6 years and 11 months old.

As mentioned in Section 1, childhood psoriasis is very prevalent, and an alternative to topical corticosteroid therapy in a pediatric population would be a desirable option. Calcitriol is a corticosteroid-sparing treatment that does not cause known steroid-related side effects such as skin atrophy and hypothalamo-pituitary axis (HPA) suppression.

PK/PD data from adolescent subjects 12-17 years of age in study SPR.18102 are mentioned in Section 1 above, including abnormalities observed in PTH levels in a subset of subjects. PTH will be monitored regularly throughout this study and all abnormal values and downward trends will be reviewed by the study Medical Expert and/or CSO. In addition, an IDMC will be in place for the duration of the study and will monitor laboratory and pharmacodynamic data as defined in the IDMC Charter.

In controlled clinical trials in adults, hypercalcemia was observed in 24% (18/74) of subjects exposed to calcitriol 3 mcg/g ointment, and in 16% (13/79) of subjects exposed to vehicle. However, the increases in calcium and albumin-adjusted calcium levels were less than 10% above the upper limit of normal.

In the two pooled 8-week vehicle-controlled studies in 419 adult subjects, pruritus and discomfort pain were reported in 1% and 3% respectively for subjects treated with calcitriol 3 mcg/g ointment, and 1% and 2% respectively for subjects exposed to vehicle.

In a 52-week open label study of 324 adult subjects, adverse events reported at a rate of greater than or equal to 3% of subjects treated with calcitriol 3 mcg/g ointment were lab test abnormality (8%), urine abnormality (4%), psoriasis (4%), hypercalciuria (3%), and pruritus (3%). Kidney stones were reported in 3 subjects and confirmed in two.

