- The PTH returns to the normal reference range but falls below the lower limit of normal at any other stage during the course of the study

then the IDMC will be contacted for advice on management.

Subjects with abnormal serum albumin-adjusted calcium should temporarily discontinue study drug use immediately. The IDMC will be consulted for each occurrence of hypercalcemia, and depending on the severity and/or duration of the out-of-range serum calcium, will recommend appropriate management of the subject on a case-by-case basis in combination with other lab values and clinical condition of the subject in general.

Subjects with suspected kidney stones should temporarily discontinue study drug and will be referred to their Primary Care Physician (PCP) for care in tandem with Sponsor consultation of the IDMC. If urolithiasis is not confirmed, the subject may resume treatment with study drug. Subjects with confirmed urolithiasis should permanently discontinue study drug use and complete the Week 26/ET visit.

A subject who has been enrolled and assigned a kit number cannot be replaced by another subject if he/she discontinues the clinical trial for any reason.

For subjects not completing the entire study, all used (and unused) study drugs containers should be returned by the subject's parent/legal guardian to the defined personnel at the study center.

GALDERMA may also decide to prematurely terminate or suspend a subject's participation in the clinical trial.

Potential reasons for discontinuation, as listed on the Exit Form, are defined below:

- **Pregnancy:** **Withdraw the Subject from the clinical trial and follow the procedure described in Section 7.2.3.2.4**
- **Lack of Efficacy:** Investigator judgment only: based on therapeutic/disease-state expectations. If subject/parent or legal guardian opinion only, mark "subject request" and document it in the comment section of the eCRF Exit Form.
- **Adverse Event:** Complete an Adverse Event Form.
- **Subject Request:** Includes consent withdrawal, subject relocation, schedule conflicts. Explain the reason for withdrawal in the comment section of the eCRF Exit Form.
- **Protocol Violation:** Explain the violation in the comment section of the eCRF Exit Form.
- **Lost to Follow-up:** Confirmed with two documented phone calls and a certified letter (delivery receipt requested) without answer. Explain in the comment section of the eCRF Exit Form.

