### 7.1.1.2 *Pruritus (as evaluated on all treated areas)*

Pruritus will be evaluated at each visit and scored on a 0 to 4 point scale. The following definitions will be used to score Pruritus:

**Pruritus:** an itching sensation.

0	None	No itching
1	Mild	Slight itching, not really bothersome
2	Moderate	Definite itching that is somewhat bothersome without loss of sleep
3	Severe	Intense itching that has caused pronounced discomfort, night rest interrupted
4	Very Severe	Very severe itching that has caused pronounced discomfort during the night and daily activities

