7.3.2 Adverse Events

Adverse events will be coded using the Medical Dictionary for Regulatory Activities (MedDRA) dictionary (version 15.0).

Treatment-emergent adverse events (TEAEs) is defined as an AE with an onset date on or after the first application of the study drug. TEAEs will be tabulated in frequency tables by System Organ Class and Preferred Term for whole study and by period (Day 1 to Day 90, Day 91 to End of Treatment, Follow-up period). Additional summary tables will be provided for TEAEs that are considered serious (SAEs), related to the study drug(s), severe, and possibly related to Calcium Metabolism from predefined SOCs/HLGT . TEAEs of special interested and TEAEs leading to discontinuation will also be summarized. For a given TEAE, a subject will be counted once even if he/she has experienced multiple episodes of that particular TEAE. Subgroup summaries of TEAEs will be provided based on gender, race, and age group (2-5 years, 6-12 years, 13-17 years) when appropriate.

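### The AE severity scale has no criterion for laboratory abnormalities, and no planned table counts subjects by their worst on-treatment value

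*Protocol*

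**What the plan says.** - **Severity scale (Protocol 7.2.3.1.6).** One three-grade scale serves all AEs. Mild is "Awareness of signs or symptom, but easily tolerated", Moderate is "Discomfort, enough to cause interference with usual activity" and Severe is "Incapacitating with inability to work or perform usual activity". The definitions are offered as guidance and the investigator's medical judgment sets the grade. No grade refers to a laboratory value.
- **When a laboratory value is an AE (Protocol 7.2.2 and 7.2.3.1.1).** An out-of-range value is reported if it points to disease or organ toxicity or is judged pathological, and is new or worse since screening. Symptoms are not required.
- **Key safety endpoints (Protocol 9.1.1.2, SAP 4.2).** Albumin-adjusted calcium, urine calcium:creatinine ratio, phosphorus and PTH, together with adverse events.
- **AE tables (SAP 7.3.2 and 9.3).** "Additional summary tables will be provided for TEAEs that are considered serious (SAEs), related to the study drug(s), severe"; SAP 9.3 also lists AEs by maximum severity.
- **Laboratory outputs (SAP 7.3.3 and 7.5).** Descriptive statistics by visit, a Screening-versus-Final shift table in three categories, listings of out-of-range and clinically significant results, mean-change and spaghetti plots, and box plots for PTH and the calcium/creatinine ratio.
- **How size is described elsewhere.** Protocol 5.6 has the IDMC advise "depending on the severity and/or duration of the out-of-range serum calcium". Protocol 1.3 says of the adult data that "the increases in calcium and albumin-adjusted calcium levels were less than 10% above the upper limit of normal".
- **Pruritus.** AESI item 3 (Protocol 7.2.3.1.3) covers "Dermatological events such as severe skin irritation as well as severe local and/or generalized pruritus" and names no scale. Protocol 7.1.1.2 labels score 3 Severe and score 4 Very Severe, the latter defined as "Very severe itching that has caused pronounced discomfort during the night and daily activities".

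**The concern.** The main safety question is what the ointment does to calcium metabolism over 26 weeks. A reader will look for how many children had an excursion and how large it was. The AE severity grade is the usual tabulated measure of how bad an event was, but for a laboratory AE without symptoms this scale gives the investigator nothing to grade against. About 30 centers (Synopsis) may then give the same calcium value different grades, or tend towards the lowest. That would matter less if a laboratory table counted subjects by their worst value, but none is planned. A short severe-TEAE table could then be taken as reassurance about calcium that it cannot give.

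The pruritus wording is a smaller, separate matter. The same word has different meanings on two scales in the protocol, and whether an expedited AESI report is due can depend on which one is meant.

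**Working it through.** **1. The scale against a laboratory AE.** Take a new, pathological albumin-adjusted calcium in a child without symptoms. It is reportable under Protocol 7.2.2. It causes no discomfort and no lost activity, so it meets the wording of neither Moderate nor Severe. Only the investigator's judgment can place it higher, and no laboratory anchor is supplied for that judgment.

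**2. The shift table.** SAP 7.3.3 compares Screening with Final in three categories. SAP 7.5 takes Final from the last scheduled on-treatment visit first and uses unscheduled samples only where scheduled data are missing. Protocol 5.6 and 6.4 provide for a temporary stop of study drug when adjusted calcium is abnormal. Follow one illustrative child:

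| Sample | Adjusted calcium | Used in shift table? |
|---|---|---|
| Screening | within range | yes |
| Week 4 | 1.20 x ULN (illustrative) | no |
| Unscheduled repeat, drug stopped | within range | no |
| Week 12 | within range | no |
| Week 26 | within range | yes, as Final |

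The child is counted as within range at both ends.

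**3. The by-visit summary.** With 100 subjects sampled, one child at 1.20 x ULN instead of 1.00 x ULN moves the Week 4 mean by 0.20/100 = 0.002 x ULN. The by-visit maximum would show that value if it is the largest at a scheduled visit, but not how many subjects were out of range or by how much. A peak seen only at an unscheduled visit enters no by-visit summary when scheduled data exist.

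**4. Adult hypercalcemia as a scale of the problem (Protocol 1.3).** Calcitriol 18/74 = 24.3%; vehicle 13/79 = 16.5%. These are laboratory findings, not AEs. If the calcitriol rate applied to 100 children (the protocol's target; the SAP still says 140), about 24 would have at least one raised value. The shift table would show anywhere from 0 to 24 of them as above range, depending on how many had resolved by Final. If all increases stayed under 10% above ULN, as in adults, a worst-value table would show about 24 above ULN to 1.10 x ULN and 0 above that. That zero would inform on size; an empty severe-TEAE table would not.

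**5. Expected severe counts.** Inputs are the adult 52-week AE rates in Protocol 1.3: laboratory test abnormality 8%, pruritus 3%. The share graded Severe, *s*, is not in the documents and is varied. Expected count = 100 x rate x *s*; P(at least one) = 1 - (1 - rate x *s*)^100.

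| *s* | Laboratory: expected | P(at least one) | Pruritus: expected | P(at least one) |
|---|---|---|---|---|
| 0 | 0 | 0 | 0 | 0 |
| 10% | 0.8 | 0.55 | 0.3 | 0.26 |
| 25% | 2 | 0.87 | 0.75 | 0.53 |
| 50% | 4 | 0.98 | 1.5 | 0.78 |

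The laboratory count is driven by *s*, which is what the scale leaves open. Severe pruritus AEs are few on most assumptions, so a low count there could not be attributed to the wording.

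**6. The word severe for pruritus.** Score 4 describes pronounced discomfort by night and in daily activities, which is closer to AE Moderate than to AE Severe. On the pruritus scale, scores 3 and 4 both qualify as severe. AESI item 3 does not say which scale applies.

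**The case against.** The grades are guidance under medical judgment, so an investigator may grade a large calcium excursion above Mild. The key laboratory endpoints are reported from the values themselves: statistics by visit with minimum and maximum, listings, spaghetti plots, and a calcium-metabolism TEAE table that does not depend on grade. Hypercalcemia goes to the IDMC case by case. Protocol 5.6 and 1.3 speak of the size of a calcium value without invoking the AE grade, so they do not contradict the scale. Pruritus is tabulated by category and shift in SAP 7.2.5.

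All of this stands, and it rules out three stronger readings that a reader might infer:

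- *An asymptomatic laboratory AE must be Mild whatever its value.* The medical-judgment clause says otherwise.
- *The severe-TEAE and severe-pruritus counts are near zero by construction.* Symptomatic AEs can be graded Severe, AESI item 3 can be read on the pruritus scale's own labels, and no figure in the documents supports a near-zero count.
- *The AESI table cannot show a calcium excursion.* AESI item 2 takes any out-of-range result judged clinically significant and related to study drug, at any grade. Item 5 likewise sets no severity condition.

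What the objection does not answer is the missing count. Listings and plots show individual values but give no n (%), the calcium-metabolism table counts events without their size, and the box plots omit serum calcium. Judgment without an anchor also leaves consistency between centers open.

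**Conclusion.** The concern holds in limited form. The severity scale has no laboratory criterion, so the severe-TEAE and maximum-severity tables may under-represent asymptomatic laboratory events or grade them inconsistently. No planned table counts subjects by worst on-treatment value, and the shift table can miss an excursion that has resolved by Final. The key values are still collected and listed; what is missing is a summary on a key safety endpoint.

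The size cannot be fixed. It ranges from nothing, if few excursions occur or all persist to Final, to about 24 of 100 subjects with a raised calcium absent from the shift table's above-range cell. The upper figure assumes that the adult rate carries over to children and that every case resolves. The range of 0 to 4 severe laboratory AEs assumes the adult 8% AE rate and a severe share of 0 to 50%. Inconsistent grading between centers is a risk inferred from the wording; the documents contain no data on it.

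The ambiguity in AESI item 3 is a wording matter with little expected effect on counts.

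**What to change.** 1. **Add one table to SAP 7.3.3 and 9.3, for reporting only:** n (%) of subjects by worst on-treatment value, scheduled and unscheduled samples included, with temporary drug stops counted as part of the treatment period.
   - Albumin-adjusted calcium: up to ULN; above ULN to 1.10 x ULN; above 1.10 x ULN. The 10% is a descriptive cut taken from Protocol 1.3, not a clinical threshold.
   - PTH, phosphorus and urine calcium:creatinine ratio: worst value against the reference range.
   - PTH also: n (%) with the 30% fall from Baseline already used in Protocol 5.6 and 7.2.2.1. Serum PD is sampled at Baseline only in the PK group (about 9 subjects), so use Screening as the reference where there is no Baseline sample.
   - Give the number of on-treatment samples per subject. Subjects on the earlier schedule had Week 8 and Week 20 visits, and more samples give more chances of an extreme.
2. **State in SAP 7.3.2** that the severe-TEAE tables are not to be read as evidence on the size of laboratory changes.
3. **In Protocol 7.2.3.1.3, item 3,** name the scale that defines severe pruritus, so that 7.1.1.2 and 7.2.3.1.6 are reconciled.

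The cost is one derived table and some wording, with no new data and no change to any dosing or stopping rule. The downside is that some transient excursions become visible and need comment in the report. Regrading laboratory AEs by distance from the limit, or making a pruritus score an AESI trigger, is not needed for this. The latter would also turn an efficacy score into a 24-hour safety report.

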#### 7.2.3.1.7 *Relationship to the study drug(s)*

The Investigator is to determine whether there is a reasonable causal relationship between the study drug(s) and the AE. Medical judgment should be used to determine the relationship, considering all relevant factors including the pattern of reaction, temporal relationships, positive dechallenge or rechallenge, relevant medical history, and confounding factors such as co-medication or concurrent diseases.

The expression "reasonable causal relationship" is meant to convey in general that there are facts or arguments to suggest a causal relationship (ICH E2A, Section IIIA 1).

The relationship assessment for an AE is to be completed using the following definitions as a guideline for all AEs occurring during clinical trials conducted or sponsored by GALDERMA:

**Reasonable possibility:**

According to the reporting Investigator, there is a reasonable possibility (i.e., suggestive evidence or arguments) that there is a causal relationship irrespective of the dose administered between:

- The study drug (investigational product, active comparator, or placebo/vehicle, etc.) and the AE,
- The clinical trial protocol procedure (such as UV-induction, biopsy, xylocaine injection, blood test or intraocular pressure measurement, etc) and the AE.

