**No Reasonable Possibility:**

No suggestive evidence or arguments can be identified regarding a causal relationship between the study drug or the clinical trial protocol procedure and the AE.

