**7.2.3.2 Reporting procedures**

**7.2.3.2.1 Procedures for reporting Adverse Events**

The collection of AEs is from the time that a subject signs the ICF to their final visit.

At each post-enrollment visit, the Investigator (or sub-Investigator) will question the subject about AEs using an open non-persuasive question to elicit reporting of AEs, for example “Have you noticed any change in your health since the last visit?” Directed questioning and examination will then be performed as appropriate.

Any AE occurring during the AE reporting period, whether it is related to the study drug(s) or not, will be recorded immediately in the source document, and described on the Adverse Event Form of the eCRF along with the date of onset, severity, relationship to the study drug(s), and outcome, without omitting any requested and known information. Additional information may be requested under certain circumstances. Adverse Events (AEs) assessed as related to the treatment will be monitored until they are completely or satisfactorily resolved. Other AEs will be monitored until the last visit if they are not resolved or satisfactorily resolved.

The Investigator will obtain and maintain in the subject’s files all pertinent medical records, information and medical judgment from colleagues who assisted in the treatment and follow-up of the subject. If necessary, the Investigator will contact the subject’s personal physician or hospital staff to obtain further details.

For SAEs (see Section 7.2.3.2.2), AESIs (see Section 7.2.3.2.3), cases of urolithiasis and pregnancies (see Section 7.2.3.2.4), the CSO is to be informed immediately by e-mail/fax. The event must be reported by fax or sent by e-mail to the CSO within 24 hours of receipt of the information (contact details in Section 7.2.3.2.2).

7.2.3.2.2 *Procedure for reporting a Serious Adverse Event*

For an SAE occurring during the period of the clinical trial, regardless of whether it is related to the treatment or not, and of whether it is expected or not, the Investigator must do the following:

1. Take prompt and appropriate medical action, if necessary. The safety of the subject is the first priority.
2. Immediately inform the CSO of the event by e-mail or by fax and discuss further actions to be taken.

Clinical Safety Officer

For North America: Phone: (+1) [contact] - Fax: (+1) [contact]

E-mail: [[contact]](mailto:[contact])

For EU: [contact] – [contact]

E-mail: [[contact]](mailto:[contact])

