### 9.1.5 Safety analysis methods

No inferential statistical analysis is planned for safety endpoints of the study.

The laboratory parameters at scheduled visits and change from Screening at post-baseline visit(s) will be summarized descriptively by treatment and by visit. A shift table for lab parameters at Screening versus Week 26/ET will be provided when appropriate.

Only Treatment-emergent Adverse Events (TEAEs) will be summarized. A TEAE is defined as an AE with an onset date on or after the first application of the study drug.

TEAEs will be tabulated in frequency tables by System Organ Class and Preferred Term based on the Medical Dictionary for Regulatory Activities (MedDRA). Additional summary tables will be provided for TEAEs that are considered serious (SAEs), related to the study drug(s), and severe. TEAEs that are AESIs, as well as TEAEs leading to discontinuation will also be summarized. For a given TEAE, a subject will be counted once even if he/she has experienced multiple episodes of that particular TEAE. Subgroup summaries of TEAEs will be provided based on gender, age group, and race when appropriate.

Prior and concomitant therapies and procedures will be summarized. A prior therapy/procedure is one that ends at or before baseline; and a concomitant therapy/procedure is one starting after the baseline visit.

Extent of study drug exposure and compliance will also be summarized.

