3.2.1 Adverse Events (AE)

Adverse events (AEs) are to be monitored throughout the course of the clinical trial (from the subject signed the Informed Consent Form to the end of the subject's participation). All AEs are to be reported on the Adverse Event Form of the eCRF with complete information as required, including onset/end dates of AEs, severity of AEs, relationship to the study drug, serious AEs and AEs of special interest.

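### The causality definitions combine study drug and protocol procedure, so a blood-draw event can be counted as drug-related in the TEAE tables

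*Protocol*

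**What the plan says.** Protocol Section 7.2.3.1.7 is headed as relationship to the study drug and opens with a drug-only question: "The Investigator is to determine whether there is a reasonable causal relationship between the study drug(s) and the AE". It then gives two categories for the assessment.

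- *Reasonable possibility* has two limbs. The first is "The study drug (investigational product, active comparator, or placebo/vehicle, etc.) and the AE". The second is "The clinical trial protocol procedure (such as UV-induction, biopsy, xylocaine injection, blood test or intraocular pressure measurement, etc) and the AE".
- *No Reasonable Possibility* requires that nothing suggests a "causal relationship between the study drug or the clinical trial protocol procedure and the AE".

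The later uses refer to the drug alone. Protocol Section 7.2.3.2.1 has the AE form completed "along with the date of onset, severity, relationship to the study drug(s), and outcome". SAP Section 3.2.1 lists "severity of AEs, relationship to the study drug, serious AEs and AEs of special interest". For the summaries, Protocol Section 9.1.5 says "Additional summary tables will be provided for TEAEs that are considered serious (SAEs), related to the study drug(s), and severe", and SAP Section 7.3.2 says "Additional summary tables will be provided for TEAEs that are considered serious (SAEs), related to the study drug(s), severe". The table list in SAP Section 9.3 has drug-related AE tables and a listing, and no table for procedure-related events. Nothing in either document names a procedure-relationship item or says how *related* is derived from the two categories.

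**The concern.** The definitions are wider than the question they serve. If the eCRF holds one relationship item scored with these two categories, bruising or fainting caused purely by a blood test satisfies the second limb of *Reasonable possibility* and fails the condition for *No Reasonable Possibility*. It would then pass into a table presented as drug-related events.

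The trial has one arm and no inferential analysis, so no control group shows the background of procedure events, and the any-related percentage is read at face value. Relatedness also decides how long an event is followed: under Section 7.2.3.2.1, events related to treatment are followed to resolution and others only to the last visit. An event placed in the wrong category therefore also falls under the wrong follow-up rule.

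**Working it through.** **Step 1: the texts side by side**

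| Place | Causes covered |
|---|---|
| Protocol 7.2.3.1.7, heading and opening sentence | Drug |
| Protocol 7.2.3.1.7, *Reasonable possibility* | Drug, or procedure (blood test named) |
| Protocol 7.2.3.1.7, *No Reasonable Possibility* | Neither drug nor procedure |
| Protocol 7.2.3.2.1 and SAP 3.2.1, items named for the AE form | Drug |
| Protocol 9.1.5, SAP 7.3.2 and SAP 9.3, summaries | Drug |

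There are two categories only. For an event caused by a blood draw and not by the drug, the condition for *No* is not met, because there is evidence for the procedure. The condition for *Reasonable possibility* is met through its second limb. Under a single item the definitions leave no other answer.

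**Step 2: what must hold for a miscount**

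(a) The eCRF has one causality item. (b) *Related* in the tables is derived from *Reasonable possibility*. (c) The investigator follows the second limb and not the heading and opening question. The documents settle none of these.

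**Step 3: which draws count**

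A TEAE needs onset on or after the first application (Protocol 9.1.5, SAP 7.3.2), so events with onset before it, such as those from screening draws, do not enter. Table 2 and Appendix 2 of the current protocol leave Weeks 4, 12 and 26 for every subject, so k = 3. Week 30 makes k = 4. It is mandatory for the PK group (about 9 of 100) and at the investigator's discretion for the others.

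**Step 4: size, as an illustration only**

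The documents give no rate of procedure events and no expected rate of drug-related events, so there is no stated figure to reproduce. Let q be the assumed chance of a reportable AE per draw. With independent draws, the share of subjects with at least one such event is s = 1 − (1 − q)^k. The expected number among 100 subjects is 100 × s.

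| q (assumed) | k = 3 | k = 4 |
|---|---|---|
| 0.1% | 100 × (1 − 0.999³) = 0.3 | 100 × (1 − 0.999⁴) = 0.4 |
| 1% | 100 × (1 − 0.99³) = 3.0 | 100 × (1 − 0.99⁴) = 3.9 |
| 5% | 100 × (1 − 0.95³) = 14.3 | 100 × (1 − 0.95⁴) = 18.5 |

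The k = 4 column treats every subject as drawn at Week 30 and is an upper case. With 91 subjects at k = 3 and 9 at k = 4, q = 1% gives 91 × 0.0297 + 9 × 0.0394 = 3.06.

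Subjects who continue under the original protocol (Protocol 10.5.2) may follow the schedule still shown in the SAP, which adds serum draws at Weeks 8 and 20. That makes k = 5 before any Week 30 draw, and q = 1% then gives 100 × (1 − 0.99⁵) = 4.9 per 100. The number of such subjects is not stated.

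**Step 5: effect on the any-related percentage**

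Take a true drug-related share r = 5% (assumed), independent of draw events, and k = 3. The pooled share is 1 − (1 − r)(1 − s):

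- q = 0.1%: 1 − 0.95 × 0.9970 = 5.3%
- q = 1%: 1 − 0.95 × 0.9703 = 7.8%
- q = 5%: 1 − 0.95 × 0.8574 = 18.5%

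The effect runs from negligible to material, and the documents do not say where it lies. All these figures also suppose that every draw event is scored *Reasonable possibility*, so they are ceilings for a given q.

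**The case against.** The strongest reply is that the governing instruction is drug-only. The heading and opening sentence of Section 7.2.3.1.7 say so, the definitions are offered as a guideline subject to medical judgement, and an investigator completing an item labelled as relationship to the study drug would have to disregard that label to score a venepuncture bruise as related. The two limbs can also be read as one scale applied to two separate questions. UV-induction and intraocular pressure measurement are not in this trial's schedule, which suggests general sponsor wording. The lists in Protocol 7.2.3.2.1 and SAP 3.2.1 are not complete descriptions of the form, so their silence does not prove that a procedure item is absent.

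Most of this stands against a stronger reading. A reader might infer that blood-draw events do inflate the drug-related table. The documents do not support that, because the eCRF is not among them and conditions (a) to (c) are all open.

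A reader might also infer a rise as large as the drug signals, by setting it beside the adult pruritus and discomfort rates of 1 to 3% in Protocol Section 1.3. That comparison fails. Those are reported rates, not drug-related rates, and the per-draw rate here is assumed. The tables are also by System Organ Class and Preferred Term, so fainting or a puncture-site bruise would appear under its own term and leave the pruritus or hypercalciuria rows unchanged.

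The reply does not remove the contradiction. *No Reasonable Possibility* joins drug and procedure in one condition, which fits a single scale. Even if the eCRF has two items, neither document says which one feeds the related tables.

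**Conclusion.** The point holds as a contradiction in the text: the definitions cover drug or procedure, while the question, the named AE-form item and the tables cover drug only. Followed literally under one item, they allow a pure blood-draw TEAE to be counted as drug-related. Actual misclassification is not shown.

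The size is unknown and probably small. Under the current protocol it rests on 3 mandatory post-application draws, or 4 with Week 30, and on an assumed per-draw rate. Per 100 subjects the illustration runs from 0.3 (q = 0.1%, k = 3) to 18.5 (q = 5%, k = 4). The upper end needs one draw in 20 to yield a reportable AE and every such event to be scored against the label of the item. The overall any-related percentage is the figure mainly exposed. Any error would overstate drug-related events. The laboratory key safety endpoints (calcium, urine calcium:creatinine ratio, phosphorus and PTH) are untouched.

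A reader might further infer that AESI counts are distorted. The two items in Section 7.2.3.1.3 that depend on relatedness also require a clinically significant out-of-range laboratory result, or a cutaneous event leading to discontinuation of study drug. Fainting meets neither, and a bruise would qualify only if study drug were stopped for it. The effect there is slight.

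**What to change.** 1. In Protocol Section 7.2.3.1.7, limit the definitions used for relationship to study drug to the study-drug limb, in both categories.
2. Record procedure causality as a separate item, or confirm that the eCRF already does so.
3. State in SAP Section 7.3.2 that the related-TEAE tables use the study-drug judgement only, and how *related* is derived from the recorded category.
4. Before lock, query procedure-type events already coded *Reasonable possibility*, so that the investigator confirms causality for each. The data review meeting can identify these events but should not reclassify them itself.

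The cost is minor wording changes, a site memo and a few queries. No further assessments of subjects are needed.
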